8.1.2 Handling of Missing/Incomplete AE start/stop dates

Incomplete/missing start dates of AEs will be estimated by the following rules:

- If the year is missing, default to the same year the patient received the first dose of study medication, or the stop year (when the stop year is not missing) whichever occurred earlier. For an enrolled patient without using study medication, default to the same year the patients was enrolled, or the stop year (when the stop year is not missing) whichever occurred earlier;
- If the month is missing:
 - If the start year equals to the stop year, then default to the first dose month or stop month whichever occurred earlier;
 - Otherwise, default to the first dose month or enrollment month for an enrolled patient without using study medication;
- If the day is missing:

Protocol 156-13-211

Laboratory measurements that signal the potential for Hy’s Law will be reported. An incidence table and a listing will be provided for subjects who meet one or combinations of following criteria, without initial findings of cholestasis (ALP activity > 2 × ULN):

- ALT or AST ≥ 3 × ULN
- Bilirubin ≥ 2 × ULN

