5.5 Follow-up of Adverse Events

For this trial, AEs will be followed up for 7 days after the last dose of tolvaptan has been administered (follow-up period).

Subjects experiencing SAEs should be followed clinically until their health has returned to baseline status, or until all parameters have returned to normal, or have otherwise been explained.

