5.5.1 Follow-up of Nonserious Adverse Events

Nonserious AEs that are identified on the last scheduled contact must be recorded on the AE eCRF with the current status noted. All nonserious events that are ongoing at this time will be recorded as ongoing on the eCRF.

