While Trial 156-13-210 remains blinded, subjects enrolling from any prior trial besides Trial 156-08-271 are scheduled to have monthly hepatic monitoring for the first 18 months of this trial. After that, following the approval of the medical monitor, hepatic monitoring will take place every 3 months. Subjects enrolling from Trial 156-08-271 will have hepatic monitoring every 3 months. All Trial 156-13-210 subjects who are eligible for this trial will initially be scheduled to have trial visits and hepatic monitoring monthly for the first 18 months, then every 3 months thereafter, because their tolvaptan exposure cannot be determined since Trial 156-13-210 is a double blind trial. Once unblinding occurs, it can be determined which subjects received tolvaptan in Trial 156-13-210. These subjects may have their trial visits/hepatic transaminase monitoring changed to every 3 months sooner as their previous tolvaptan exposure in Trial 156-13-210 can count towards the 18-month threshold. Subjects from prior tolvaptan trials other than Trial 156-08-271 will have monthly trial visits/ALT level assessments for the first 18 months. After that, the trial visits/ALT monitoring will be conducted every 3 months after the change in frequency is confirmed with the medical monitor.

[figure not shown]
Enrollment in this trial will be closed when the last eligible subject from Trial 156-13-210 enrolls in this trial.

The duration of this trial is planned to continue

- Until the last subject from Trial 156-13-210 completes 18 months of tolvaptan treatment in this trial
- Subjects enrolling from other trials will conclude their participation once tolvaptan becomes available through routine prescription or through a compassionate use or named-patient program). Trial 156-13-210 subjects may opt to conclude their participation in this trial if tolvaptan becomes available before they complete 18 months of treatment in this trial

The study schema, presented in [Figure 3.1-1](#), depicts the overall study design.

Protocol 156-13-211

Figure 3.1-1 Study Design and Treatment Schema -Extension Study

Note: FU=follow-up

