3.4 Trial Visit Window

Due to the extended duration of the study, the individual patient data will be summarized by period.

For assessments recorded at clinic visits, except for the hepatic monitoring for the subjects from Trial 156-08-271, data will be derived by mapping the study day of the assessment into corresponding time windows as specified in [Table 3.4.1](#). Study day is calculated as: date of assessment - date of enrollment (ie, screening or baseline date) + 1. If there are multiple observations within the same study time window, only the last observation within that study week will be used for the summary tables. The time window mapping rules are applicable to all post first dose safety and efficacy assessments (unless otherwise stated) that are assessed at the scheduled or unscheduled visits (excluding early termination visits/end of treatment visits).

Table 3.4.1 Mapping of clinic visit assessments to study month (except for hepatic monitoring for Subjects from Trial 156-08-271)

Study Month	Study Day Interval
Monthly Visit	
Month 1	2 – 46
Month 2	47 – 76
Month 3	77 – 107
Month 4	108 – 137
Month 5	138 – 168
Month 6	169 – 198
Month 7	199 – 229
Month 8	230 – 259
Month 9	260 – 290
Month 10	291 – 320
Month 11	321 – 351
Month 11	352 – 381
Month 13	382 – 412
Month 14	413 – 442

Protocol 156-13-211

Month 15	443 – 473
Month 16	474 – 503
Month 17	504 – 534
Month 18	535 – 595
Every 3 Months	
Month 21	596 – 686
Month 24	687 – 778
Month 27	779 – 869
Month 30	870 – 961
Month 33	962 – 1052
Month 36	1053 – 1144
Month 39	1145 – 1235
Month 42	1236 – 1327
Month 45	1328 – 1418
Month 48	1419 – 1510
Month 51	1511 – 1601
...	...

Note: Early Termination/End of Treatment (\pm 7 days)

Once Trial 156-13-210 unblinding occurs, it can be determined which subjects received tolvaptan in Trial 156-13-210. These subjects may have their trial visits/hepatic transaminase monitoring changed to every 3 months sooner as their previous tolvaptan exposure in Trial 156-13-210 can count towards the 18-month threshold.

For assessments for hepatic monitoring recorded at clinic visits, for the subjects from Trial 156-08-271, data will be derived by mapping the study day of the assessment into corresponding time windows as specified in [Table 3.4.2](#).

Study Month	Study Day Interval
Every 3 Months (\pm 45 days)	
Month 3	2 – 137
Month 6	138 – 229
Month 9	230 – 320
Month 12	321 – 412
Month 15	413 – 503
Month 18	504 – 595
Month 21	596 – 686
Month 24	687 – 778
Month 27	779 – 869

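### When an adverse event's start month is missing, SAP 8.1.2 uses the calendar month of first dose even in later years, which can date an on-treatment event after the last dose

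*SAP*

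**What the plan says.** SAP 8.1.2 has two branches for a missing adverse event start month.

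- Start year equal to stop year: "If the start year equals to the stop year, then default to the first dose month or stop month whichever occurred earlier".
- All other cases, which on a literal reading include an ongoing event with no stop year: "Otherwise, default to the first dose month or enrollment month for an enrolled patient without using study medication".

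Neither branch compares the start year with the first-dose year, and neither visible branch is capped at last dose or last contact. The available text breaks off after "If the day is missing", so the day rule, the stop-date rules and anything else in the rest of 8.1.2 cannot be read.

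Related provisions:

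- SAP 3.1 keeps the trial running "Until the last subject from Trial 156-13-210 completes 18 months of tolvaptan treatment in this trial", and the visit windows in SAP 3.4 are listed to Month 51 and beyond.
- Protocol 5.5 states that "AEs will be followed up for 7 days after the last dose of tolvaptan".
- Protocol 5.5.1 says of the last scheduled contact: "All nonserious events that are ongoing at this time will be recorded as ongoing on the eCRF".
- SAP 6.5 sets a missing start month for concomitant medications to January.
- The five adverse event incidence summaries in SAP 8.1.1 are all based on TEAEs. The available text of both documents expands that abbreviation but gives no window for it.

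**The concern.** The first-dose month is a sensible default in the first-dose year, because it is the earliest month in which an event can be on treatment. In any later year it is an arbitrary calendar month. Treatment of 18 months always crosses at least one year-end, so later years are routine in this trial.

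In a year that lies wholly within treatment, the arbitrary month affects only the onset date. In the final treatment year it can lie after the last dose. It can even lie after the contact at which the event was recorded, which is an impossible date. Long-term safety is the trial's only stated objective, so a date rule that can move on-treatment events outside treatment deserves correction even if it is seldom used.

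**Working it through.** The plan gives no figure to reproduce. The check applies the visible month rule literally.

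**Example.** First dose October 2014, last dose March 2016, start year 2016, start month missing, ongoing, participation ended at last dose.

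1. There is no stop year, so the second branch applies and the month is October.
2. The imputed onset is October 2016.
3. Even with last dose on 31 March and onset on 1 October, the gap is about six months, far beyond the 7-day follow-up in Protocol 5.5.

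**Same-year branch.** With the same doses, a stop in March 2016 gives the earlier of October and March, which is March 2016, so there is no error. A stop in December 2016 gives October 2016, the same error. Such late stop dates are possible because Protocol 5.5.2 follows serious events until they resolve.

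**Fixed treatment length.** Let m be the first-dose month (1 to 12), D the treatment length in months (12 or more), and r the remainder of D divided by 12. The event starts in the last-dose year, its start month is missing and it has no stop date.

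- If m + r is 12 or less, the last-dose month is m + r, and the imputed month m is not later than that.
- If m + r exceeds 12, the last-dose month is m + r − 12, which is less than m, so the imputed month falls after the last dose.

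The rule therefore fails when m is greater than 12 − r, that is for r of the 12 first-dose months.

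| Treatment length (months) | r | First-dose months that fail | Share |
|---|---|---|---|
| 12, 24, 36 | 0 | none | 0/12 |
| 15 | 3 | October to December | 3/12 |
| 18 | 6 | July to December | 6/12 |
| 21 | 9 | April to December | 9/12 |

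In failing cases the imputed month is 12 − r months after the last-dose month: 9, 6 and 3 months at 15, 18 and 21 months of treatment. All of these exceed 7 days whatever the day of the month. In the 0/12 rows the imputed month equals the last-dose month.

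**Onset error in a full later year**, if the true onset month is uniform over January to December:

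- First-dose month as default, with first-dose month also uniform and independent: mean absolute error = 572/144 = 3.97 months.
- January as default: (0 + 1 + … + 11)/12 = 66/12 = 5.5 months, always early.

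**January in the last-dose year.** The imputed month is never later than the last-dose month, so the failures are 0/12 at every length in the table.

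**The case against.** A reader might infer that these events drop out of the TEAE tables. The documents do not support that. It would need a TEAE window closing at or soon after last dose, and no window appears in the available text. The 7 days in Protocol 5.5 are an adverse event follow-up period. If TEAE means any onset after first dose, the event stays in all five summaries and only its date is wrong.

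The unseen part of 8.1.2 also matters. If the stop-date rules give ongoing events a stop at last contact, the example moves to the first branch and becomes March 2016, on treatment. A cap could also be there. Text that is absent from the public copy is not a defect in the plan.

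It is tempting to quote a single failure rate. With first-dose and last-dose months independent and uniform it would be 66/144 = 46%, but the documents give no basis for that assumption, and the table shows that the result turns on treatment length.

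It is also tempting to stress events that lead to discontinuation. Those are immediately reportable under Protocol 5.1. Protocol 5.3 asks for serious ones within 24 hours of awareness and for nonserious ones that require discontinuation within 3 working days. A known year with a missing month should be rare for them.

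Finally, January gives a larger average onset error than the present rule. That stands, so the case for January is that it keeps events within treatment; it does not date onset better.

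What survives is narrower: the visible rule has no year condition and can produce an onset after the last dose.

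**Conclusion.** The concern holds as a minor defect in a stated rule. For a start year after the first-dose year, the visible month default carries no information. In the final treatment year it can place an on-treatment event after the last dose, and after trial exit if participation ended then. For the treatment lengths checked, the share of first-dose months affected runs from 0/12 to 9/12, with 6/12 at 18 months. These shares apply only to events with a known year, a missing month, onset in the last-dose year and no stop date that triggers the other branch.

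The number of such events is not given and is probably small. An effect on TEAE counts is possible but not established. It depends on the TEAE window and the stop-date rules.

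**What to change.** Amend SAP 8.1.2 as follows:

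- Use the first-dose month only when the start year is the first-dose year.
- For a later start year with a missing month, impute January of that year, as SAP 6.5 does for concomitant medications, and never a date later than the stop date.
- State the TEAE window beside the rule, and count as a TEAE any event whose known date parts are compatible with on-treatment onset.

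If the full SAP already contains a cap or a stop-date rule that prevents the problem, confirming this would be enough.

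The cost is a few sentences and a small programming change. The downside is early bias in onset for these few events, about 5.5 months on average in a full later year if the true month is uniform. Imputed onset dates should therefore be flagged and not used for timing.

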2.1 Trial Rationale

Evidence from previous studies suggests that during the first 18 months of long-term treatment in subjects with ADPKD, ALT and/or aspartate aminotransferase (AST) elevations and evidence of idiosyncratic DILI occurs at a greater frequency in tolvaptan treated subjects. However, the rate of new transaminase elevations beyond 18 months and up to 4.5 years was similar between tolvaptan treatment and placebo subjects.

Over the 3 years of placebo-controlled treatment, ALT was elevated to a greater than three times the upper limit of normal ($> 3 \times \text{ULN}$) in 4.4% of tolvaptan subjects compared with 1% of placebo subjects. To date, 3 tolvaptan subjects' transaminases and bilirubin levels reached Hy's laboratory criteria ($> 3 \times$ and $> 2 \times \text{ULN}$, respectively). Upon discontinuation, all subjects' liver tests showed reversibility of the elevation within approximately 4 months after tolvaptan was discontinued. Nevertheless, without adequate monitoring and management, it is estimated that a 1:4,000 risk for irreversible liver injury may exist.

Through more frequent (eg, monthly) monitoring of liver transaminases, the current trial will more precisely define the potential for DILI previously observed in Trial 156-04-251. Frequent monitoring will also detect smaller elevations earlier permitting closer and more thorough evaluation and intervention (including drug interruption or discontinuation). This is expected to mitigate the risk of serious or irreversible injury.

CCI [Redacted text block]

Protocol 156-13-211

CCI

This trial will extend our understanding of tolvaptan's long-term safety in ADPKD patients.

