3.4.3 Exclusion Criteria

Subjects will be excluded if they meet any of the exclusion criteria in [Table 3.4.3-1](#).

1.	WOCBP who do not agree to practice 2 different methods of birth control or remain abstinent during the trial and for 30 days after the last dose of IMP. If employing birth control, 2 of the following precautions must be used: vasectomy of partner, tubal ligation, vaginal diaphragm, intrauterine device, birth control pill, birth control implant, birth control depot injection, condom, or sponge with spermicide.
2.	Women who are breast-feeding and/or who have a positive pregnancy test result prior to receiving IMP.
3.	Need for chronic diuretic use.
4.	Hepatic impairment based on liver function abnormalities other than that expected for ADPKD with cystic liver disease during screening based on recent historical laboratory values (in the last 3 months).
5.	Subjects with contraindications to required trial assessments (contraindications to optional assessments, eg, MRI are not a limitation).
6.	Subjects who, in the opinion of the investigator or medical monitor, have a medical history or medical finding inconsistent with safety or trial compliance. This includes prior evidence of significant hepatic injury deemed to be related to tolvaptan use.

WOCBP=women of childbearing potential; IMP=investigational medicinal product

Non-childbearing potential in women is defined as female subjects who are surgically sterile (ie, have undergone bilateral oophorectomy or hysterectomy) or female subjects who have been postmenopausal for at least 12 consecutive months.

Subjects may be rescreened, at the discretion of the medical monitor, if the exclusion characteristic has changed or resolved. In the event that a subject is rescreened, a new ICF must be signed and a new screening number assigned and screening procedures repeated.

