3.5 Trial Endpoints

3.5.1 Safety Endpoints

This trial will have no formal endpoints. Safety variables will be summarized by descriptive statistics, (eg, proportion, mean, median, standard deviation [SD], minimum, and maximum values). In general, summary statistics, including changes from baseline, will be provided for safety variables based on all available data. Safety endpoints will be as follows:

- Adverse events
- Vital signs

Protocol 156-13-211

- Clinical laboratory assessments
- Serum transaminase elevations for frequency (2x, 3x, 5x and 10x ULN), time to onset, time to peak levels, time of offset (< 3x, 2x, or 1x ULN), response to de-challenge and re-challenge and frequency of progression to Hy’s laboratory criteria (ALT or AST > 3x ULN and bilirubin, total (BT), > 2x ULN without alkaline phosphatase ≥ 2x ULN)
- Serum sodium excursions above 145, 150, or 155 mmol/L or below 135, 130, or 125 mmol/L

CCI [REDACTED]

[REDACTED]

[REDACTED]

CCI [REDACTED]

[REDACTED]

[REDACTED]

[REDACTED]

[REDACTED]

[REDACTED]

[REDACTED]

[REDACTED]

[REDACTED]

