6.6 Protocol Deviations

Protocol deviations occurring to patients will be listed and summarized (only for major protocol deviations) by patient type by parent trial.

7 Efficacy Analysis

No efficacy analyses are planned.

8 Safety Analyses

Safety analysis will be conducted based on the Safety Population, which is defined as all subjects in the Enrolled Population who take at least one dose of IMP. Safety variables to be analyzed include clinical laboratory tests, vital signs, and AEs. CCI [REDACTED]

In general, baseline measurements of safety variables are defined as the last measurements prior to the first dose of IMP in Trial 156-13-211. Safety variables will be summarized by descriptive statistics, (eg, proportion, mean, median, SD, minimum, and maximum values). Summary statistics, including changes from baseline, will be provided for safety variables based on all available data. No inferential statistical analyses of the safety variables will be performed.

Safety variables to be analyzed include:

- Adverse events
- Vital signs
- Clinical laboratory assessments
- Serum transaminase elevations for frequency (2x, 3x, 5x and 10x ULN), time to onset, time to peak levels, time of offset (< 3x, 2x, or 1x ULN), response to de-challenge and re-challenge and frequency of progression to Hy's laboratory criteria (ALT or AST > 3x ULN and bilirubin, total (BT), > 2x ULN without alkaline phosphatase > 2x ULN)
- Serum sodium excursions above 145, 150, or 155 mmol/L or below 136, 130, or 125 mmol/L

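### The SAP's potential Hy's Law table drops isolated ALT/AST or bilirubin elevations when ALP exceeds 2 × ULN, and its cut-offs differ from the protocol's without being declared

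*SAP*

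**What the plan says.** Protocol 3.5.1, in both the main and the UK versions, defines Hy's laboratory criteria as "ALT or AST > 3x ULN and bilirubin, total (BT), > 2x ULN without alkaline phosphatase ≥ 2x ULN". The synopsis uses the same limits.

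The list of safety variables in SAP Section 8 keeps the transaminase and bilirubin limits but writes the ALP limb as "without alkaline phosphatase > 2x ULN".

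Further on in SAP Section 8, just before 8.3 Vital Signs Data, a separate paragraph plans an incidence table and a listing of laboratory values that point to possible Hy's Law. It covers "subjects who meet one or combinations of following criteria, without initial findings of cholestasis (ALP activity > 2 × ULN"), and the two criteria are "ALT or AST ≥ 3 × ULN" and "Bilirubin ≥ 2 × ULN".

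SAP Section 13 records no changes to the planned analyses.

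**The concern.** Two things are wrong.

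- **Three sets of cut-offs for one concept.** Progression to Hy's laboratory criteria is a named safety variable. A programmer working from the SAP finds strict inequalities in the variable list and non-strict ones in the table paragraph. Neither ALP limb matches the protocol, and Section 13 does not mention this.
- **The reach of the ALP condition.** In the protocol, ALP qualifies only the combination of raised transaminase and raised bilirubin. In the SAP paragraph it qualifies one or both criteria. An isolated ALT elevation is then removed because ALP is also raised.

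Protocol 2.1 gives closer definition of the potential for drug-induced liver injury as a purpose of the trial. The table and listing that collect possible Hy's Law signals should therefore not leave out subjects through a condition the protocol does not attach to single elevations.

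**Working it through.** The plan has no figure to reproduce. The trial is descriptive, and the sample size was not set by a power calculation. The check compares the definitions as logical rules, with all values in multiples of ULN.

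**Rules**

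| Source | ALT/AST | Bilirubin | Excluded if ALP |
|---|---|---|---|
| Protocol 3.5.1 | > 3 | and > 2 | ≥ 2 |
| SAP 8, variable list | > 3 | and > 2 | > 2 |
| SAP Hy's paragraph, both criteria | ≥ 3 | and ≥ 2 | > 2 (initial) |
| SAP Hy's paragraph, either criterion | ≥ 3 | or ≥ 2 | > 2 (initial) |

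**Grid.** Each rule was applied to values just below, at and just above each cut-off: ALT 2.9, 3.0, 3.1; bilirubin 1.9, 2.0, 2.1; ALP 1.9, 2.0, 2.1. That gives 3 × 3 × 3 = 27 profiles.

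| Rule | Profiles flagged |
|---|---|
| Protocol 3.5.1 | 1 |
| SAP 8, variable list | 2 |
| SAP paragraph, both criteria | 8 |
| SAP paragraph, either criterion | 16 |
| ALT > 3 and bilirubin > 2, ALP ignored | 3 |

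**Combined criterion.** If ALT > 3, bilirubin > 2 and ALP < 2, then also ALT ≥ 3, bilirubin ≥ 2 and ALP ≤ 2. Every protocol case therefore meets both SAP versions. The SAP paragraph adds 8 − 1 = 7 profiles, and each has at least one value exactly on a cut-off. The SAP is the more inclusive, and only at equality.

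**Single criteria.** Of the 9 ALT and bilirubin pairs, 8 meet at least one criterion. Ignoring ALP, that is 8 × 3 = 24 profiles. With the ALP condition it is 8 × 2 = 16, so 24 − 16 = 8 are removed, all with ALP 2.1:

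- 4 meet both criteria; the protocol's own ALP limb would exclude these too.
- 2 have ALT alone (3.0 or 3.1, bilirubin 1.9).
- 2 have bilirubin alone (2.0 or 2.1, ALT 2.9).

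The last two groups, 4 profiles, are removed only because the SAP extends the ALP condition to single criteria.

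**Size, as an illustration.** SAP Section 4 expects about 2,500 subjects. Protocol 2.1 reports ALT > 3 × ULN in 4.4% of tolvaptan subjects over 3 years of placebo-controlled treatment. Carried over unchanged, 2,500 × 0.044 = 110 subjects. The documents give no rate of ALP > 2 × ULN among such subjects, so it is varied:

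| Assumed share with ALP > 2 × ULN | Subjects missing from the table |
|---|---|
| 1% | 110 × 0.01 = 1.1 |
| 5% | 110 × 0.05 = 5.5 |
| 10% | 110 × 0.10 = 11 |
| 20% | 110 × 0.20 = 22 |

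The 4.4% may not carry over, because many subjects enter after earlier tolvaptan exposure. The 110 would also include any subjects whose bilirubin was raised as well.

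**The case against.** The best defence is that the paragraph describes a broad screen for possible Hy's Law, separate from the endpoint count. The variable list in SAP Section 8 carries that count with the protocol's transaminase and bilirubin limits, and only the sign on ALP differs. Subjects missing from the screen are not lost to the report. Transaminase elevations at 2, 3, 5 and 10 × ULN are summarised with no ALP condition, and the Appendix 1 grades for ALT, AST and bilirubin have none. The triggers for the liver case report form in Protocol 3.7.2.4.2 do not depend on a normal ALP either. They feed a blinded adjudication whose results go to the data monitoring committee at least quarterly.

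Most of this stands, and it keeps the severity down. It does not explain why a broad screen should exclude isolated elevations on ALP. Adjudication is also not a full substitute within the study report, since Protocol 3.7.2.4.2 allows its results to be presented separately.

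A further caution is that the available SAP text breaks off within 8.1.2 and resumes at the Hy's paragraph. Text that cannot be seen might qualify the wording. For that reason the lack of a visible time window pairing ALT with bilirubin, or of a definition of the initial ALP finding, is not counted here as an omission. Protocol 3.5.1 sets no window either; the word concurrent belongs to the rule on resuming treatment in 3.7.2.4.1.

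**Conclusion.** The point holds in a limited form. The cut-offs are inconsistent and undeclared, but for the combined criterion this matters only at exact equality, and no protocol-defined case is lost. The substantive fault is that the SAP paragraph, followed as written, removes isolated ALT/AST or bilirubin elevations with ALP > 2 × ULN from the potential Hy's Law table and listing. Severity is minor to moderate. The count affected is unknown; the range of about 1 to 22 rests on the assumed 4.4% and the assumed ALP shares.

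Three stronger readings are tempting, and the documents do not support them:

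- **The SAP loses genuine Hy's cases.** Take ALP 2.3, ALT 6 and bilirubin 3 × ULN. Protocol 3.5.1 already excludes this subject from the combined count. What the SAP adds is removal from the single-criterion rows.
- **Subjects with liver cysts vanish from the main hepatic results.** The entry criterion, "Hepatic impairment based on liver function abnormalities other than that expected for ADPKD with cystic liver disease during screening", lets such subjects enrol. Neither document says that cystic liver disease raises ALP above 2 × ULN, and the other summaries still count these subjects.
- **The count cannot be set beside the 3 earlier cases.** Protocol 2.1 says their transaminase and "bilirubin levels reached Hy's laboratory criteria" and gives no ALP limb. That is background shorthand and does not show how the cases were classified. No such comparison is planned.

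**What to change.** In the SAP:

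1. Use the Protocol 3.5.1 definition for the count of progression to Hy's laboratory criteria, both in the Section 8 variable list and in the Hy's paragraph. Otherwise, state the difference and the reason in Section 13.
2. Apply the ALP condition only to the combined row of ALT/AST plus bilirubin. Tabulate and list single-criterion elevations whatever the ALP.
3. Show the combined row twice, with and without the ALP condition, so that subjects with raised ALP who meet both limbs stay visible.

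A fixed window for pairing ALT and bilirubin (30 days, for example) and an ALP rule relative to the subject's own screening value are optional preferences and not part of this point.

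The cost is a change of SAP wording and one extra table row, with no new data. The downside is that the reported count may be slightly higher.
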